# 1. Introduction

# 1.1 Background

Suboptimal cardiometabolic health is on a disproportional rise in Low- and Middle-Income Countries (LMICs). In sub-Saharan Africa (SSA), cardiometabolic dysfunction is being exacerbated by the ongoing nutrition transition, that has seen a change from traditional diets to fast and ultra processed foods rich in sugar, fats, and salt coupled by low physical activity (1). Similarly, chronic inflammatory diseases such as HIV can aggravate cardiometabolic risks (2). HIV aetiology and Antiretroviral Therapy (ART) have been shown to exacerbate metabolic syndrome. Although the pathophysiology remains rather elusive, HIV triggers glucose metabolism dysregulation and dyslipidaemia. In part, this is linked to the inflammation triggered by viral infection. The virus triggers chronic activation of the innate immune system with excessive production of inflammatory cytokines. These inflammatory mediators increase the risk of atherosclerosis and insulin resistance (2). Our recent study among people living with HIV (PLWH) under community-based HIV care model in Uganda revealed a high prevalence of metabolic syndrome (28%), central obesity (44.5%), raised fasting blood glucose (49.6%), hypertriglyceridemia (26.4%), low HDL-c (56.7%), and high blood pressure (31.5%). This cardiometabolic dysfunction is compounded by low quality carbohydrate-based diets devoid of fruits and vegetables (3). Fruits and vegetables are the bedrock of a healthy diet (4, 5). However, although WHO recommends a daily intake of at least 5 servings a day (6), in our

<sup>1 Department of Food Science and Technology, Kyambogo University, Kampala, Uganda

<sup>2 Clinical and Experimental Endocrinology, Department of Chronic Diseases and Metabolism, KU Leuven, Leuven, Belgium

<sup>3 Nutrition unit, Department of Health Sciences, School of Applied Sciences, Mildmay Institute of Health Sciences, Kampala, Uganda

<sup>4Department of Endocrinology, University Hospitals Leuven, Leuven, Belgium

\*Corresponding author; [contact]

study the average intake of fruits and vegetables was just 1.5 servings and a low polyphenol intake (212 mg) (3).

Beyond conventional nutrients, fruits and vegetables have ubiquitous amounts of bioactive components including polyphenols, alkaloids, saponins, and terpenes and terpenoids, with polyphenols being the most ubiquitous of all. Dietary polyphenols are a diverse category of secondary plant metabolites that represent the largest group of naturally occurring antioxidants with cardioprotective benefits (7-9). A daily 5 servings intake of fruits and vegetables coincides with 500-1000 mg of total polyphenols, a threshold that is considered beneficial for cardiometabolic homeostasis (10). Our recent meta-analysis demonstrated that an average intake of 780 mg/d of total polyphenols significantly reduced blood pressure, total cholesterol, triglycerides, and improved vascular function (11). The (poly)phenolic composition of fruits and vegetables can vary considerably according to the region of growth among other factors (9, 12). For example, Africa's Indigenous Fruits and Vegetables (IFV) have been shown to contain high concentrations of polyphenols (13, 14). Our recent inventory study of Uganda's IFV with purported cardiometabolic benefits, highlighted the popularity of *Tamarindus indica* as a local adjuvant therapy for cardiometabolic risks among Ugandan communities (15). The study also revealed that the polyphenol composition of *T. indica* is superior in 4755mg/100g FW in relation to other IFV identified.

*T. indica,* is a leguminous tree belonging to the family Fabaceae with a wide range of bioactive constituents in varying levels- the highest being polyphenols followed by alkaloids, saponins, and terpenoids in that order (16). The principal flavonoids in *T. indica* fruit pulp are composed of flavanols especially the oligomeric procyanidins and their monomers- epicatechins and catechins (17, 18). Recent dietary guidelines for bioactives recommend a daily intake of 400-600 mg of flavanols for cardiometabolic protection (19) while the European Food Safety Authority (EFSA) recommends that 200 mg/d intake of cocoa flavanols is important for vascular homeostasis (20). Elsewhere, the COSMOS study showed that an intake of 500 mg/d of flavanols averts 27% of CVD mortality with significant reduction in CVD events (21). Flavanol increases the endothelial production and bioavailability of nitric oxide, a signalling molecule for endothelial function (20).

A potential mechanism of action by which polyphenols confer hypotensive effects is by increasing the bioavailability of nitric oxide (NO) and upregulating endothelial NO-synthase activity. NO is a potent vasodilator that reduces blood pressure. Additionally, flavonoids

especially flavanols may block angiotensin converting enzyme (ACE) activity, reducing blood pressure. In fact, flavanols, anthocyanins, phenolic acids, tannins, and resveratrol have been identified as green ACE inhibitors (11).

Although the benefits of the community-based HIV care model in the resource limited HIV management settings are well documented, in Uganda, the lack of dietary interventions promoting cardiometabolic health could obscure such benefits (22-24). Lifestyle modifications such as programmed physical activity, weight loss, and dietary adjustments are indispensable to optimal cardiometabolic health (25, 26). However, the existence of a health-beauty paradox in SSA could thwart such interventions premised on maintaining a healthy body weight. The health-beauty paradox is a socio-cultural positive perception where a large body size is construed as a sign of prosperity and freedom from HIV (27). Moreover, dietary approaches that aim to add a healthy food portion on to one's habitual diet rather than completely changing their menu are by far more culturally diffusible (28). Therefore, we aim to evaluate the efficacy of *T. indica* fruit juice (added to patients' usual diets) on selected cardiometabolic risk markers of PLWH under the community-based HIV care model in Uganda in a proof-of-concept clinical trial. Evidence could lead to the concomitant use of such food products as adjuvant therapies in the secondary prevention of cardiometabolic risks.

### 1.2. Hypotheses

The hypotheses are:

H1: Consumption of *T. indica* fruit juice will result into an overall improvement in cardiometabolic (vascular function, blood pressure, glycaemic, and lipidemic) response.

 $H_2$ : There will be differences in the dose-response relationship in cardiometabolic control following the intake of increasing doses of polyphenols in *T. indica* fruit juice.

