### 2. Materials and Methods

#### 2.1.1 Intervention food materials

Two blinded juice prototypes of 10% and 30% fruit pulp packaged in amber bottles each consisting of 300mls will be supplied by the Uganda Natural Chemotherapeutics Research Institute. The chemical and phytochemical characteristics of the test juice are presented in table 1.

Table 1: Chemical and phytochemical characteristics of *Tamarindus indica* fruits juice

Fruit juice prototypes (pulp %)	TPC (GAE, mg/100ml)	TFC (RE, mg/100ml)	TT (GAE, mg/100ml)	Alkaloids (%)	Brix	Ph	TTA (g of tartaric acid/100ml)	Antioxidant potential, IC50, µL
10%	8.30	6.75	8.30	0.34	6.80	3.28	0.35	36.71
30%	26.36	12.29	10.17	0.44	6.80	2.89	0.95	37.46

TPC, Total Polyphenols Content; TFC, Total Flavonoids Content; TT, Total Tannins; TTA, Titratable acidity

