### 2.2 Study design and participants

This is a single centre, 2-arm, 4 weeks randomised, double-blinded parallel trial with equal allocation ratios (1:1). We will follow the Consolidated Standards of Reporting Trials (CONSORT) recommendations for randomized trials (32). Participants will be PLWH (30-60 years) managed under the community-based model (Community Drug Distribution Points-CDDPs) in Wakiso district, central Uganda. The district encircles Kampala, Uganda's capital city with an estimated population of over 2.9 million people. The district has the highest prevalence (10%) of HIV in Uganda. Over 3,801 PLWH are currently receiving the HIV care from CDDPs in Wakiso District (33). The study inclusion and exclusion criteria are presented in Table 2. The study will be announced during the drug refill days and interested patients will be provided with more information about the study before obtaining their consent to participate.

Demographic and medical information will be collected from all consented patients,

[figure not shown]
The study participants will be randomly allocated to consume twice-daily 300 mL of either 10% or 30% pulp of T. indica fruit juice, **figure 1**. Both participants and the study team will be blinded to the intervention materials. Measurements will be performed at three different timelines: 1) Baseline, 2) Week two of the study, and 3) Endline (week four of the study).

Compliance to the study protocol will be confirmed by weekly telephone inquiries, and by counting the returned empty juice bottles or unused study products at each follow-up visit. Participants will be asked to maintain their habitual dietary regimen.

Any reported unusual gastrointestinal side effects, including abdominal pain/cramps, heartburn, stomach acid/reflux, nausea, vomiting, abdominal rumbling, bloating, belching, excess gas/wind, stool type, etc, during the study will be recorded. Patients will be encouraged to contact a study staff by phone or e-mail if they experience any adverse health-related impacts of the interventions. In the case of *T. indica* fruit juice intolerance, patients will be excluded.

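### The aim and H1 concern the effect of drinking the juice, but both arms drink it, so the trial can test only 30% against 10% pulp

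*Combined protocol and SAP*

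**What the plan says.** Section 1.1 states the purpose as "Therefore, we aim to evaluate the efficacy of" *T. indica* juice taken on top of what patients usually eat, and looks ahead to practice: "Evidence could lead to the concomitant use of such food products as adjuvant therapies in the secondary prevention of cardiometabolic risks". H1 in section 1.2 says that consumption of *T. indica* "fruit juice will result into an overall improvement in cardiometabolic (vascular function, blood pressure, glycaemic, and lipidemic) response". H2 concerns dose: "There will be differences in the dose-response relationship in cardiometabolic control following the intake of increasing doses of polyphenols in" the juice.

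Section 2.1.1 lists the products: "Two blinded juice prototypes of 10% and 30% fruit pulp". Section 2.2 describes a two-arm parallel trial, allocated 1:1, with participants "randomly allocated to consume twice-daily 300 mL of either 10% or 30% pulp of T. indica fruit juice". On timing it says "Measurements will be performed at three different timelines", namely baseline, week two and week four. The text nowhere calls the 10% juice a control or a placebo.

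Table 2 requires triglycerides (TG) of at least 150 mg/dL at entry, and section 2.3.1 makes change in TG the primary endpoint. Section 6 names a Student t-test between groups. It brings in linear mixed models only to deal with missing data, and specifies no time effect or within-arm contrast. It mentions neither hypothesis.

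**The concern.** The aim and H1 ask what happens when people drink the juice, compared with not drinking it. The design randomises people between two strengths of the same juice. Nobody is randomised to go without, so the protected comparison answers a different question from the one in the aim.

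The consequence lies in what can be concluded. If the two arms end up alike, the trial has no randomised evidence on whether both juices helped or neither did. The pressure will then be to read any fall from baseline as efficacy, and H1 as worded invites that reading. Section 1.1 points towards adjuvant use, so a claim wider than the randomised contrast could be carried into practice.

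**Working it through.** The plan gives no sample size, effect size or power, so there is no stated figure to reproduce. The check has three parts.

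**1. What the randomised contrast estimates.** Let e10 and e30 be the mean effects of each juice on TG change relative to no juice. Let b be the change that would occur without juice (time, taking part in a trial, regression to the mean). Under randomisation b has the same expectation in both arms.

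- Expected change, 10% arm: e10 + b
- Expected change, 30% arm: e30 + b
- Between-arm difference: (e30 + b) − (e10 + b) = e30 − e10

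H1 is about e10 and e30 themselves. If e30 = e10 and both are beneficial, the difference is 0. If e30 = e10 = 0, the difference is also 0. In either case a valid test at section 6's 0.05 level rejects in about 5% of trials, whatever the sample size. No numerical assumption is needed. If e30 is better than e10, the test gives direct, randomised evidence that added pulp has an effect, but it estimates neither e30 nor e10.

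**2. Whether change from baseline could serve H1.** The three visits would allow it to be computed. Within an arm it estimates e + b, and pooled over equal arms it estimates (e10 + e30)/2 + b. Nothing in the design removes b. Because entry requires TG of at least 150 mg/dL and TG is the primary endpoint, b may include regression to the mean. Sizing it would need the spread of TG, its correlation between visits, and whether the qualifying value also serves as baseline. The text gives none of these, so no figure is put on it.

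**3. How far the 10% juice is from zero dose, in composition.** On the juices, section 2.1.1 says "The chemical and phytochemical characteristics of the test juice are presented in table 1". Volume is 2 × 300 = 600 mL/day, so each value per 100 mL is multiplied by 6.

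| Component | 10% juice | 30% juice | Difference | 10% / 30% |
|---|---|---|---|---|
| Total polyphenols, mg/day | 8.30 × 6 = 49.8 | 26.36 × 6 = 158.2 | 108.4 | 31.5% |
| Total flavonoids, mg/day | 6.75 × 6 = 40.5 | 12.29 × 6 = 73.7 | 33.2 | 54.9% |
| Titratable acidity, g/day | 0.35 × 6 = 2.1 | 0.95 × 6 = 5.7 | 3.6 | 36.8% |
| Brix | 6.80 | 6.80 | 0 | 100% |

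The low arm is plainly not a zero dose. Tannins and alkaloids are left out on purpose. In the 10% row, tannins and total polyphenols have the same value, 8.30, which may be a transcription slip (in the 30% row tannins are 10.17/26.36 = 38.6% of polyphenols). The basis of the alkaloid percentage is not stated.

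**The case against.** The strongest defence is that the 10% juice works as a low-dose control. Section 1.1 describes 500–1000 mg/day of polyphenols as a beneficial threshold. The 10% arm's 49.8 mg/day is only 5.0% to 10.0% of that. If the response has a threshold, the 10% juice could be nearly inert and the contrast could come close to the full effect of the 30% juice. This stands as a possibility, but the documents do not show it. The 30% arm, at 158.2 mg/day, is itself below that threshold (15.8% to 31.6%), and the protocol never assigns the 10% juice the role of control.

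The same uncertainty bars the opposite overstatement. A reader might infer from Table 1 that the contrast recovers a known share of the juice-versus-none effect, such as 108.4/158.2 = 68.5% if polyphenols drive it or 33.2/73.7 = 45.1% if flavonoids do. Those shares assume one active component and a straight line through zero. A saturating response would lower them and a threshold would raise them, so no range should be stated. Likewise, equal Brix might suggest that any sugar effect cancels between arms. Brix counts all soluble solids and the acidity differs (0.35 versus 0.95 g/100 mL), so equal sugar is not shown.

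Two further points stand in the plan's favour. The test that section 6 names is a fair test of its own contrast, and no within-arm efficacy test is announced. Section 6 ties no analysis to H2 either, so its silence on H1 reflects general brevity. Proof-of-concept status may excuse the absent power calculation, but it does not let a 30%-versus-10% comparison answer a question about drinking the juice.

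**Conclusion.** The point holds, and the aim and H1 are wrong as written for this design. The only randomised contrast is 30% versus 10% pulp, a difference of 108.4 mg/day in total polyphenols. It addresses H2 at two dose levels and cannot test H1. This follows from the arms and the named test alone. Figure 1 is not available, but the text on two arms and two pulp levels leaves no room for a juice-free group.

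The conclusion is about the scope of the claim. A reader might infer that the planned between-arm analysis is biased, or that a benefit of 30% would mean little. Neither is supported: the comparison is randomised, and such a result would be direct evidence for added pulp. The doses rest on Table 1 and full intake of 600 mL/day. The bias in a before-after reading, and the share of the juice-versus-none effect that the contrast captures, cannot be sized from the documents.

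**What to change.** Restate the aim (section 1.1) and H1 (section 1.2) as a comparison of 30% with 10% pulp *T. indica* juice on TG (primary) and on the secondary outcomes of Table 3. Align H1 with H2, since two arms give one dose contrast. Add to section 6:

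*The between-arm difference is the only test of effect. Within-arm or pooled changes from baseline, including any time effect from the mixed model, are descriptive and are not evidence of efficacy. A null between-arm difference does not show that either juice works.*

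This changes wording only, with no new arm and no more patients. The price is a narrower claim: an effect of added pulp instead of efficacy of the juice.

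Keeping H1 as a tested efficacy claim would need a randomised comparator without *T. indica* pulp. A juice-free arm would test the whole drink, but its participants could not be blinded. A matched pulp-free drink could be blinded but would test the pulp only. As a third parallel arm at 1:1:1, either needs 3/2 = 1.5 times the patients at the same number per arm. At a fixed total, the standard error of each pairwise contrast rises by a factor of √1.5 = 1.22. That is a larger design change and is not the recommended fix.

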### 2. Materials and Methods

#### 2.1.1 Intervention food materials

Two blinded juice prototypes of 10% and 30% fruit pulp packaged in amber bottles each consisting of 300mls will be supplied by the Uganda Natural Chemotherapeutics Research Institute. The chemical and phytochemical characteristics of the test juice are presented in table 1.

Table 1: Chemical and phytochemical characteristics of *Tamarindus indica* fruits juice

Fruit juice prototypes (pulp %)	TPC (GAE, mg/100ml)	TFC (RE, mg/100ml)	TT (GAE, mg/100ml)	Alkaloids (%)	Brix	Ph	TTA (g of tartaric acid/100ml)	Antioxidant potential, IC50, µL
10%	8.30	6.75	8.30	0.34	6.80	3.28	0.35	36.71
30%	26.36	12.29	10.17	0.44	6.80	2.89	0.95	37.46

TPC, Total Polyphenols Content; TFC, Total Flavonoids Content; TT, Total Tannins; TTA, Titratable acidity

### 2.2 Study design and participants

This is a single centre, 2-arm, 4 weeks randomised, double-blinded parallel trial with equal allocation ratios (1:1). We will follow the Consolidated Standards of Reporting Trials (CONSORT) recommendations for randomized trials (32). Participants will be PLWH (30-60 years) managed under the community-based model (Community Drug Distribution Points-CDDPs) in Wakiso district, central Uganda. The district encircles Kampala, Uganda's capital city with an estimated population of over 2.9 million people. The district has the highest prevalence (10%) of HIV in Uganda. Over 3,801 PLWH are currently receiving the HIV care from CDDPs in Wakiso District (33). The study inclusion and exclusion criteria are presented in Table 2. The study will be announced during the drug refill days and interested patients will be provided with more information about the study before obtaining their consent to participate.

Demographic and medical information will be collected from all consented patients,

[figure not shown]
The study participants will be randomly allocated to consume twice-daily 300 mL of either 10% or 30% pulp of T. indica fruit juice, **figure 1**. Both participants and the study team will be blinded to the intervention materials. Measurements will be performed at three different timelines: 1) Baseline, 2) Week two of the study, and 3) Endline (week four of the study).

Compliance to the study protocol will be confirmed by weekly telephone inquiries, and by counting the returned empty juice bottles or unused study products at each follow-up visit. Participants will be asked to maintain their habitual dietary regimen.

Any reported unusual gastrointestinal side effects, including abdominal pain/cramps, heartburn, stomach acid/reflux, nausea, vomiting, abdominal rumbling, bloating, belching, excess gas/wind, stool type, etc, during the study will be recorded. Patients will be encouraged to contact a study staff by phone or e-mail if they experience any adverse health-related impacts of the interventions. In the case of *T. indica* fruit juice intolerance, patients will be excluded.

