# 2.3.1 Study outcomes

The primary endpoint will be changes in Triglycerides (TG). Secondary outcomes will include changes in fasting blood glucose and plasma levels of lipids, and parameters of vascular function, **Table 3**.

Table 3: Study outcome measures

Primary outcome measures	Secondary outcome measures	Exploratory outcomes	
Triglycerides [mg/dL]	PWV [m/s], Blood pressure [mmHg]	BMI [kg/m²]	
	Facting Pland always [mg/dI]	Fat mass composition	
	Fasting Blood glucose [mg/dL]	Waist circumference [cm]	
	HDL-c, LDL-c, Total cholesterol [mg/dL]		
	AIx (%), MAP		

BMI, Body Mass Index; PWV, Pulse Wave Velocity; HDL-c, High Density Lipoproteins; LDL-c, Low Density Lipoproteins; AIx, Augmentation Index; MAP, Mean Arterial Pressure

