#### 10. Withdrawal of participants

Participants can withdraw from the study at any time for any reason if they wish to do so.

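### The plan commits to recording gastrointestinal effects only; it invites reports of other adverse effects but does not say they are recorded, classified or analysed

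*Combined protocol and SAP*

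**What the plan says.** Section 2.2 deals with harms in three steps.

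- What will be recorded: "Any reported unusual gastrointestinal side effects, including abdominal pain/cramps, heartburn" and further digestive symptoms. The list is open-ended, but only within the gastrointestinal system.
- What is invited: "Patients will be encouraged to contact a study staff by phone or e-mail if they experience any adverse health-related impacts of the interventions". The text does not go on to say that such a contact is written down, classified or forwarded.
- Who leaves: participants who do not tolerate the juice are excluded. Nothing says what is documented when that happens.

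Section 10 adds one sentence on leaving the trial: "Participants can withdraw from the study at any time for any reason if they wish to do so". It does not ask for the reason.

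On outcomes, section 2.3.1 makes triglycerides primary and continues: "Secondary outcomes will include changes in fasting blood glucose and plasma levels of lipids, and parameters of vascular function". Table 3 also lists blood pressure as secondary, and BMI, fat mass and waist circumference as exploratory. It lists no safety outcome. Section 6 describes the comparison of endpoint means and the handling of missing data, and does not mention adverse events.

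**The concern.** The recording rule is narrower than the effects that the plan itself anticipates. Section 1.1 sets out a blood-pressure-lowering mechanism for polyphenols, through nitric oxide and ACE inhibition, and Table 2 excludes people with very low blood pressure. Yet dizziness or fainting falls outside the one class of event that is to be recorded. A hospital admission for any non-digestive cause does too.

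The wording narrows the rule further. Digestive effects count if they are reported and unusual. Other effects are invited only as impacts of the interventions, which leaves the participant to judge cause before calling.

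At stake is what the trial can say about harm at the end. Section 1.1 says that the evidence could lead to use of such products as adjuvant therapy in people living with HIV. A reader of the results would want to know about serious and non-digestive events, and events not written down at the time cannot be reliably recovered later.

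**Working it through.** **1. Which kinds of harm information have a written recording rule?** The relevant parts of the plan, side by side:

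| Information | Where one would look | Written rule to record it? |
|---|---|---|
| Gastrointestinal effects | Section 2.2 | Yes |
| Other adverse effects | Section 2.2 | Contact invited; recording not stated |
| Serious adverse events | Sections 2.2, 7, 8 | None. Section 7 reports approvals; section 8 grants access to source data, including for ethics review. Neither requires an event to be notified |
| Reason for withdrawal | Section 10 | None |
| Details of exclusion for intolerance | Section 2.2 | None |

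One of the five has a rule. Separately, neither Table 3 nor section 6 contains a safety outcome or safety analysis. The weekly calls in section 2.2 are described as compliance checks, so they do not fill the gap as written, though they could carry the question.

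**2. Are the metabolic measures a substitute?** Only in part. Triglycerides, glucose, blood pressure and BMI are trial outcomes, and section 2.2 schedules measurements at baseline, week two and week four. Individual values will therefore exist. The planned use is a comparison of group means, which does not show how many participants worsened.

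**3. How large is the soluble-solids load, and could the planned comparison show an effect of it?** The plan states no figure for the load, so there is none to reproduce. Inputs:

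- Volume (section 2.2): participants are "randomly allocated to consume twice-daily 300 mL of either 10% or 30% pulp of T. indica fruit juice", so 2 × 300 mL = 600 mL/day in both arms.
- Brix (Table 1): 6.80 for both juices.
- Duration (section 2.2): "This is a single centre, 2-arm, 4 weeks randomised, double-blinded parallel trial", so 28 days.
- Density: not given; assumed 1.00 to 1.03 g/mL.

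Load = volume × density × Brix/100:

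- Density 1.00: 600 × 1.00 × 6.80/100 = 40.8 g/day; × 28 = 1,142 g.
- Density 1.03: 600 × 1.03 × 6.80/100 = 42.0 g/day; × 28 = 1,177 g.

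This is about 41 g/day of soluble solids, not of sugar. Table 1 gives titratable acid of 0.35 and 0.95 g/100 mL, that is 0.35 × 6 = 2.1 g/day in the 10% juice and 0.95 × 6 = 5.7 g/day in the 30% juice.

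Because Brix and volume are the same in both arms, an effect of the shared solids would be expected to cancel in the between-arm comparison. With no arm that receives no juice, it could appear only as change from baseline, without a control.

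**The case against.** The strongest reply is that the plan is brief rather than restrictive. It invites reports of any adverse impact, staff speak to participants every week and see them at follow-up visits, and a competent team would probably write down a hospital admission. Silence about recording is not an instruction to discard. Much of this is fair, and it limits the point to what the plan commits to. It does not remove the gap: when one class of event is named for recording and others are not, what is kept is left to individual staff.

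Several stronger readings are tempting, and the documents do not support them:

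- A reader might infer that worsening glucose, triglycerides or weight would be lost. They are measured as outcomes, and section 9 provides for sharing de-identified individual data. What is missing is a plan to report them as safety information.
- A reader might infer that no non-gastrointestinal event would be captured. The plan leaves recording unspecified; no capture rate follows from that.
- A reader might take the 49.6% with raised fasting glucose in section 1.1 as the share at risk here. It comes from a survey of people in community HIV care. The trial excludes people treated for diabetes, hypertension or dyslipidaemia and requires triglycerides of at least 150 mg/dL, so 49.6% is neither an estimate nor an upper bound for this sample.
- A reader might convert all the soluble solids to sugar energy. The titratable acid in Table 1 argues against that for both juices.
- A reader might see the trial as meant to establish adjuvant use. Section 1.1 calls it a proof of concept whose evidence could lead there.

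It is also fair to object that the soluble-solids load is a separate matter from adverse-event recording, and that a count of worsening by arm could not attribute harm to it. Both points stand.

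**Conclusion.** The concern holds as a gap in the written recording rule. Section 2.2 commits to recording gastrointestinal effects and leaves the recording, classification and analysis of all other adverse events unspecified, and no other section supplies the missing pieces. The trial could follow its plan fully and still have an incomplete account of harms.

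The size is qualitative: one of five kinds of harm information has a rule, and there is no safety outcome or analysis. The number of events at issue cannot be calculated, because the plan gives neither a sample size nor expected event rates. The 41 g/day of soluble solids is correct under the stated density assumption. It is context for why measured worsening deserves a look; it is not evidence of harm.

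This should be changed, though it does not threaten the primary comparison. Confidence is medium: Figure 1 is not shown and the consent pages were not available, and either might contain further recording or reporting instructions. The statement that individual worsening is in the data assumes that these measures are taken at all three time points.

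**What to change.** **In section 2.2**, widen the recording rule from gastrointestinal effects to all adverse events of any body system, from the first bottle to the week-four visit, whether or not the participant blames the juice. Ask about them with an open question at the existing weekly calls and visits. For each event record seriousness, onset, outcome and action taken. State that serious events are notified to the ethics committee.

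**In sections 2.2 and 10**, record the reason for every withdrawal and every exclusion for intolerance, while keeping the right to leave without giving one.

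**In section 6**, add a table of adverse events, serious events and reasons for leaving, by arm.

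**Optionally**, add a descriptive count, by arm and pooled, of participants whose glucose, triglycerides or blood pressure moves to a worse category than at baseline, with categories fixed before unblinding. Two limits should be printed with it. It cannot attribute worsening to the soluble solids, which are the same in both arms with no no-juice control. And because everyone enters with triglycerides of at least 150 mg/dL, a boundary at that value would show no upward movement, and later values may tend to fall through selection alone.

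The cost is some wording, one form and one or two descriptive tables, with no new visit or test. The downside is modestly more recording, including events unrelated to the juice.

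### Gastrointestinal effects are recorded only when reported and 'unusual', with no stated symptom question, baseline record or tabulation by arm, so symptoms are likely to be under-counted and unevenly captured

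*Combined protocol and SAP*

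**What the plan says.** Everything on this point is in section 2.2 of the protocol (Study design and participants).

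- **What is recorded:** "Any reported unusual gastrointestinal side effects, including abdominal pain/cramps, heartburn, stomach acid/reflux, nausea, vomiting", followed by further items such as bloating, belching and stool type. The word 'unusual' is not defined.
- **How other harms reach staff:** "Patients will be encouraged to contact a study staff by phone or e-mail if they experience any adverse health-related impacts of the interventions". The participant makes the contact.
- **Scheduled calls:** "Compliance to the study protocol will be confirmed by weekly telephone inquiries". Compliance is the only purpose given.
- **Scheduled visits:** "Measurements will be performed at three different timelines: 1) Baseline, 2) Week two of the study, and 3) Endline (week four of the study").
- **Exposure:** participants are "randomly allocated to consume twice-daily 300 mL of either 10% or 30% pulp of T. indica fruit juice".

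The available text contains no symptom questionnaire, baseline symptom record, severity grade or fixed time for asking about symptoms. Table 3 (section 2.3.1) has no tolerability outcome, and section 6 (Statistical analysis) has no safety analysis. The abbreviation key to Figure 1 has no symptom item, but the figure itself is not shown.

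**The concern.** A symptom has to pass two filters before it counts: someone must report it, and it must be considered unusual. Without a baseline record there is no reference for what is unusual in a given participant. Belching, gas and bloating are common, so participants and staff may discard them, and not all in the same way. If some callers happen to ask and others do not, the count also depends on who made the call.

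This matters because the two juices differ clearly in acidity. Gastrointestinal effects are the only kind of harm the protocol lists, and heartburn and reflux are among them. The introduction (section 1.1) looks ahead to using such products as adjuvant therapy alongside usual care, so the tolerability of the higher-pulp juice is worth knowing. A rule that misses symptoms lowers the recorded rate in both arms and shrinks any difference between them. Symptoms not recorded during the four weeks cannot be recovered reliably afterwards.

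**Working it through.** The plan states no safety figure, so there is none to reproduce. The check has two parts.

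**1. Acid load, from the documents.** Titratable acidity is the second-last figure in each row of Table 1 (section 2.1.1), in g of tartaric acid per 100 mL:

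- 10% juice: "10% 8.30 6.75 8.30 0.34 6.80 3.28 0.35 36.71", so 0.35
- 30% juice: "30% 26.36 12.29 10.17 0.44 6.80 2.89 0.95 37.46", so 0.95

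Daily volume is 2 × 300 = 600 mL in both arms, that is, six times 100 mL.

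- 10% juice: 0.35 × 6 = 2.1 g/day
- 30% juice: 0.95 × 6 = 5.7 g/day
- Ratio: 5.7 / 2.1 = 2.7
- Hydrogen-ion concentration ratio from pH 2.89 v 3.28: 10^(3.28 − 2.89) = 10^0.39 ≈ 2.5

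For comparison, the total polyphenol ratio is 26.36 / 8.30 = 3.2 and the Brix values are equal. After polyphenols, titratable acidity is the largest ratio between the juices in Table 1.

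**2. Effect of incomplete capture, by assumption only.** The documents give no sample size, symptom rate or capture fraction. Let c be the fraction of true symptoms that are recorded, equal in both arms. Recorded rates are then c × p, so the ratio between arms is unchanged and the difference becomes c × (p₂ − p₁). Power is for the two-sided Fisher exact test at p < 0.05, found by enumerating all outcomes.

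| Assumed true rates | n per arm | c = 1 | c = 0.5 | c = 0.3 |
|---|---|---|---|---|
| 40% v 15% | 40 | 64% | 27% | 10% |
| 40% v 15% | 30 | 49% | 15% | 5% |
| 40% v 15% | 20 | 32% | 11% | 4% |
| 25% v 15% | 40 | 14% | 5% | 2% |

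Expected counts for the first row are 40 × 0.40 × c v 40 × 0.15 × c: 16 v 6 people at c = 1, 8 v 3 at c = 0.5, and about 5 v 2 at c = 0.3.

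For a less common symptom, the chance of recording no case in an arm is (1 − p × c)^n. With p = 5% and n = 40:

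- c = 1: 0.95^40 = 13%
- c = 0.5: 0.975^40 = 36%
- c = 0.3: 0.985^40 = 55%

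The direction is the same in every row. The size depends entirely on the assumed inputs.

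**The case against.** Much of the case on the other side stands.

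- **Staff may ask.** A reader might infer that symptoms count only when volunteered. The text does not say so: a reported symptom can be an answer to a question, and a list that includes stool type and abdominal rumbling reads partly like things staff would ask about. What can be said is that no question is required or scripted.
- **The 'unusual' filter is not universal.** The invitation to contact staff covers any adverse health impact, without that word. The word may also be meant to separate new symptoms from habitual ones. That is a reasonable aim, but it needs a baseline record, and none is planned.
- **Blinding helps.** Participants and study team are both blinded, which makes different capture by arm less likely, and equal capture preserves the ratio of rates. It does not preserve the absolute rates or the difference.
- **Tolerability is not a stated aim.** The aim, hypotheses and Table 3 concern cardiometabolic markers. A reader might take tolerability as a main output, or gastrointestinal effects as the main expected harm. The protocol says neither and ranks no harms.
- **Intolerance cases are probably documented.** A reader might infer that exclusions for intolerance would lack any symptom record. That is weak: intolerance known to staff would normally have been reported, and so recorded. How exclusion for intolerance fits with the intention-to-treat statement in section 6 is a separate question, and those passages must be reconciled.
- **A checklist does not guarantee a detectable difference.** With 25% v 15% at 40 per arm, full capture gives only 14% power. The reason for asking everyone is uniform, interpretable counts, not a significance test.

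**Conclusion.** The point holds as a weakness in how harms are ascertained. As written, the rule is likely to give incomplete and inconsistent counts of gastrointestinal symptoms, and no comparison by arm is planned although the acid load differs 2.7-fold (5.7 v 2.1 g/day). The acid figures follow from Table 1 and the daily volume. That symptoms could differ by arm is a plausible inference from them, not a finding.

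The documents do not support saying that under-counting is certain, or putting a number on it. The power figures are an illustration that assumes the sample size, true rates and capture fraction, with capture equal in both arms; they range from 64% down to 2% over the scenarios shown. No primary or secondary result is affected. This is an inexpensive improvement best made before enrolment, not a flaw that undermines the trial.

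**What to change.** Replace the sentence on recording gastrointestinal effects in section 2.2 with the text below. It keeps the existing symptom list and drops the word 'unusual'.

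> At baseline, at each weekly call and at the week 2 and week 4 visits, all participants are asked the same fixed checklist of the gastrointestinal symptoms listed here (present or absent, severity), in addition to spontaneous reports. The number of participants with each symptom, and the number excluded for intolerance, are tabulated descriptively by randomised arm.

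No new contacts are needed. The cost is a few more minutes at each existing call or visit, one case report form page and one table. The downside is that more minor symptoms will be recorded; the baseline answers and the severity item help in reading them. If the sponsor already intends staff to ask, the change only writes that intention down and makes the asking uniform.
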